## INTRODUCTION

Breast cancer is the commonest cancer among Egyptian females (38.8%) and modified radical mastectomy (MRM) is the most common surgical intervention.

Breast cancer surgery induces marked acute nociceptive and neuropathic pain in the chest wall, axilla and ipsilateral arm. Effective postoperative balanced analgesia including regional anaesthesia suppresses the surgical stress response and diminishes opioids needs.

The commonest reasons for overnight stay after breast cancer surgeries are postoperative pain, nausea and vomiting and anxiety. Postoperative hospital stay for breast cancer patients has shortened owing to not only the less invasive surgical technique, but also the efficient pain relief protocols including regional anaesthesia.

Ultrasound-guided fascial plane blocks are novel techniques which showed effectiveness in managing post-mastectomy pain.

Erector spinae plane (ESP) block is one of the fascial plane blocks; its efficacy depends on the compartmental spread and the local anaesthetic (LA) distribution to nearby target nerves. The absorption and diffusion of the LA has a role in determining the quality of ESP block. LA may diffuse anteriorly to the ventral and dorsal rami of the spinal nerves and through the intertransverse connective tissue to enter the thoracic paravertebral space.

Local anaesthetic volume and concentration are important factors for unilateral ESPB with volumes ranging from 10 to 40 mL have been used. However, the optimum volume and concentration, distribution and dermatomal coverage is still undetermined.

As the erector spinae fascia extends from the nuchal fascia cranially to the sacrum caudally, local anaesthetic agents extend through several levels, and the block can be effective over a large area.

Cadaveric studies had been performed to assess the spread of dye in this novel block. However, not all of them have had such extensive spread of dye. In one study, only minimal spread had been observed into the paravertebral space and in another it has been failed to demonstrate any spread at all into the paravertebral space or the ventral rami but there was extensive lateral and craniocaudal spread around the Erector Spinae (ES) complex. Till now many questions about the extent of sensory coverage and if there is difference in the spread between cadavers and the living humans, as intrathoracic pressure changes may direct LA spread differently.

Post-mastectomy minimal residual may be unavoidable and the possibility for this to result in metastases and cancer recurrence relies on many factors, including anti-tumor cell mediated immunity and angiogenic and growth signals in sites of the residual. The perioperative neuroendocrine surgical stress response, volatile anaesthetics and opioids have deleterious effects on this process. In another words; the anaesthetic technique could influence perioperative immunosuppression and determine whether the immune response would be capable of eradicating the displaced tumour cells.

Natural killer (NK) cells are CD3 CD56+ lymphocytes playing a pivotal role in the innate immune response against cancer. Their main purpose is identification and eradication of virus infected cells and metastatic cells. Diminished activity of NK cells is a predisposing factor for cancer recurrence. Preservation of innate immune function and the direct anti-inflammatory effects may be the cause of the protective effects of local anaesthetics and regional techniques. Different concentrations of local anaesthetics appear to have different effects on natural killer cells (NKC) cytotoxicity. High concentrations of lidocaine suppress NK cell cytotoxicity, yet clinically relevant concentrations enhance the in vitro function of NK cells via the release of lytic granules.

## **AIM OF THE WORK**

The aim of the present study is to evaluate the effect of US guided unilateral ESPB using different volumes of local anaesthetic on analgesic efficacy, dermatomal spread and immunomodulation in breast cancer surgery.

The primary outcome is the analgesic efficacy of the different local anaesthetic volumes of ESPB.

The secondary outcomes are the dermatomal dye spread and sensory coverage, immunomodulation and complications in breast cancer surgery.

## PATIENTS

This study will be carried out on 60 female patients aged between 20-50 years, admitted to Medical Research Institute Hospital for breast cancer surgery.

All patients will be of American Society of Anesthesiology (ASA) physical status I or II, scheduled for mastectomy under the effect of general anaesthesia after taking approval of the Ethical Committee of the Faculty of Medicine, and a written consent from every patient included in the study.

The sample size is determined according to the recommendations of the department of biomedical informatics and medical statistics, Medical Research Institute using NCSS 2004 & PASS 2000 program. A minimal sample size of 15 in each group is required to estimate an average difference of 2 in the median visual analogue scale (VAS) between groups assuming common standard deviation of 2.5, using F test, at level of significance 0.05.

Patients will be randomly allocated using a computer generated random table (Graphpad Software, Inc, La Jolla, CA) and an allocation ratio of 1:1:1. Blinding of the research personnel will be maintained throughout the whole observation period including all postoperative follow-ups.

**Group (I):** 20 patients will receive US-guided deep ESPB block before induction of general anaesthesia using 20 ml bupivacaine 0.25 % and 5 ml of radiocontrast dye (Omnipaque) at the level of T4.

**Group (II):** 20 patients will receive US-guided deep ESPB block before induction of general anaesthesia using 40 ml bupivacaine 0.125 % and 5 ml of radiocontrast dye (Omnipaque) at the level of T4.

**Group (III):** 20 patients will undergo standard general anaesthesia as a control group and postoperative analgesia with intravenous morphine patient controlled analgesia (PCA) and rescue analgesia if required.

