## Measurements

The following measurements will be carried out:

**1. Patient demographics** including age, sex and weight.

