#### QUESTION 4:

In the painful area, can the pain be caused or increased by:	YES	NO
Brushing? .....		

YES = 1 point

NO = 0 points

Patient's Score: /10

Before patients would be discharged home, DN4 questionnaire will be explained to every patient. Postmastectomy neuropathic pain will be detected in breast, axilla or arm. Its onset (days) and interference with work, sleep or mood will be recorded.

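### Eligibility admits any mastectomy although the block is unilateral, and the axillary procedure is not a recorded study item: a cheap improvement, not a source of bias

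*Protocol*

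**What the plan says.** The surgical criterion in PATIENTS has two parts: women "admitted to Medical Research Institute Hospital for breast cancer surgery" who are "scheduled for mastectomy under the effect of general anaesthesia". Neither part gives the side, the type of mastectomy or whether the axilla is operated on. None of the nine exclusion criteria mentions side or axilla. Only the 90-minute limit on duration of surgery bears on surgical extent, and it does so indirectly. The INTRODUCTION remarks that "modified radical mastectomy (MRM) is the most common surgical intervention", but as background and not as an eligibility rule.

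The AIM OF THE WORK describes "US guided unilateral ESPB using different volumes of local anaesthetic", and the block technique section describes one needle approach and one catheter.

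On where the pain lies, the INTRODUCTION says that this surgery causes "marked acute nociceptive and neuropathic pain in the chest wall, axilla and ipsilateral arm". The text after the DN4 form says: "Postmastectomy neuropathic pain will be detected in breast, axilla or arm".

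Under Measurements, the patient characteristics are given as "including age, sex and weight". The other seven groups (vital signs, sedation, pain, complications, CT spread, immune outcome, satisfaction) contain no item for type of operation, side or axillary procedure. Allocation is 1:1:1 from a computer-generated table, with no stratification factor named.

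**The concern.** There are two separate gaps, and they act differently.

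**Side.** The intervention is one-sided but the population is not stated to be. VAS at rest and on movement, 24-hour morphine and rescue use are totals for the patient, not for one side of the chest. In a bilateral operation under a unilateral block, the second side would contribute to all of them unblocked. This can happen only in groups I and II, because group III has no block to miss. The effect therefore runs in one direction, towards a smaller block-versus-control difference, even when the arms are perfectly balanced.

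**Axilla.** By the protocol's own account the axilla and arm are pain sites, so whether the axilla is operated on should explain part of the between-patient variation in pain. It is neither fixed by eligibility nor listed as study data. At stake are a visible check of balance and a modest amount of precision in a trial of 20 per arm. Eligibility and the list of recorded items belong in the protocol, so this is not a matter left to an analysis plan.

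**Working it through.** **Inputs from the protocol.** 20 patients per arm; planned VAS difference 2; common SD 2.5, so variance 2.5² = 6.25; alpha 0.05. The stated minimum of 15 per group cannot be reproduced because no power is given. Only the difference and the SD are used here.

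**Assumed inputs, not in the documents.** Proportion with axillary clearance p = 0.3 to 0.7; added pain from clearance d = 1 to 2 VAS points; bilateral cases 0 to 2 of 20 in a block arm.

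**1. Dilution from bilateral cases.** If a fraction q of a block arm is bilateral and keeps a share r of the block's benefit, the expected contrast is 2 × [1 − q(1 − r)].
- q = 1/20: 1.90 if r = 0; 1.95 if r = 0.5.
- q = 2/20: 1.80 if r = 0; 1.90 if r = 0.5.
- q = 0: no effect.

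**2. Chance imbalance in axillary clearance.** With X₁ and X₂ independent binomial(20, p), the chance of a difference of 5 or more patients is:

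| p | given pair of arms | any pair of the three |
|---|---|---|
| 0.3 or 0.7 | 0.119 | 0.26 |
| 0.5 | 0.154 | 0.33 |
| 0.8 or 0.2 | 0.073 | 0.17 |
| 0.9 or 0.1 | 0.018 | 0.04 |

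The last two rows cover a hospital where one axillary approach predominates.

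**3. Size of the resulting shift.** Shift = d × 5/20 = 0.25 (d = 1) to 0.50 (d = 2). The standard error of a two-arm difference is 2.5 × √(2/20) = 0.79. The shift is therefore 0.25/0.79 = 0.32 to 0.50/0.79 = 0.63 standard errors, and 12.5-25% of the planned difference of 2.

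**4. Share of the variance.** The variance due to clearance is p(1 − p)d².
- Smallest: 0.3 × 0.7 × 1² = 0.21, and 0.21/6.25 = 3.4%.
- Largest: 0.5 × 0.5 × 2² = 1.00, and 1.00/6.25 = 16%.

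**5. What adjustment recovers.** Two-sided t test, 20 per arm, difference 2. With SD 2.5 the power is 0.69. If 2.5 is the total SD, adjustment lowers it to √(6.25 − 0.21) = 2.46 or √(6.25 − 1.00) = 2.29, and power becomes 0.71 or 0.77. If instead 2.5 is the SD within one type of operation, the unadjusted SD is √(6.25 + 0.21) = 2.54 or √(6.25 + 1.00) = 2.69. Unadjusted power is then 0.68 or 0.63, and adjustment restores it to 0.69. The protocol does not say which SD it means. Either way the covariate is worth a few points of power.

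**The case against.** The strongest reply is that the effects are small and rest on assumptions, and much of it stands.

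- A reader might infer that pain differences between arms could reflect the operation and not the block. The documents do not support that. Allocation is random, so an imbalance in axillary surgery is chance and is already covered by the nominal type I error. The assumed shift of 0.25-0.5 is below one standard error and could not alone create a 2-point difference.
- A reader might infer that imbalance could never be seen or adjusted for. That goes too far. The side must be known to place a one-sided block, and the operation note would ordinarily hold the axillary procedure. What is missing is prespecified study data, not the information itself.
- A reader might infer that stratified randomisation is required. Unstratified allocation of 60 patients is valid. Small blocks within two strata also have a cost: group III has no block and no sham is described, so staff who see allocations could more easily guess the next one.
- Nothing shows that bilateral cases would be enrolled. The protocol's framing is one-sided throughout, and the 90-minute exclusion would remove some long operations. But that exclusion does not address side and is known only once surgery is over, and framing is not an eligibility rule.
- The proportion with clearance and its effect on VAS are assumed. If one approach predominates, imbalance is rarer, as the table shows.

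The mismatch between a one-sided block and a population not limited to one side survives, as does the absence of the axillary procedure from the recorded items.

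**Conclusion.** The point holds as a cheap improvement. The eligibility wording admits bilateral mastectomy, which would dilute the block-versus-control contrast in one direction: from 2 to 1.8-1.9 if 1 or 2 of 20 block patients were bilateral without benefit, and not at all if none are enrolled. The axillary procedure bears on the protocol's own pain sites but is not among its measurements. Under the assumed 30-70% clearance and 1-2 VAS points, a 5-in-20 imbalance moves a contrast by 0.25-0.5, and the factor accounts for 3-16% of the planned variance. Adjusting for it would raise power at 20 per arm from about 0.69 to 0.71-0.77 if 2.5 is the total SD. This is lost precision and avoidable dilution. It is not systematic bias, and it does not invalidate the randomised comparison.

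**What to change.** 1. In PATIENTS, state unilateral mastectomy as an inclusion criterion.
2. Under Measurements, add side of operation and axillary procedure (none, sentinel node, clearance). Record the planned procedure before allocation and the performed one from the operation note.
3. Include planned axillary clearance (yes/no) as a covariate when comparing pain and morphine. Use the planned and not the performed procedure, so that the covariate is fixed before allocation.
4. Stratifying the random list by planned clearance is optional.

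The cost is one word of eligibility text, two added data fields and a note of the planned axillary procedure before allocation. The few bilateral cases, if any, would not be enrolled.

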**Exclusion criteria**

1. Age below 18 or more than 70.
2. Scoliosis or any vertebral anomalies or previous spinal surgeries.
3. Morbid obesity ( $BMI \geq 40 \text{ kg/m}^2$ ).
4. Allergy or contraindication to any of the studied medications or anaesthetic agents.
5. Chronic opioid analgesic use.
6. Pregnancy.
7. Infection at the site of injection or any other contraindication for regional anaesthesia.
8. Duration of surgery more than 90 minutes.
9. Renal impairment.

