## METHODS

### **Preoperative evaluation of the patients:**

Evaluation of the patients will be carried out on the day before surgery through proper history taking, clinical examination, complete blood count (CBC) and needed laboratory investigations according to the patient status. Plain X ray chest and ECG will be done for patients above 40 years. All patients will be informed with the procedure of US guided deep ESPB block and they will be trained to use the visual analogue scale (VAS) which consists of 10 cm line, 0 equivalent to no pain and 10 denoting the worst imaginable pain.

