#### 4. Pain assessment:

1. Acute postoperative nociceptive pain will be measured by:
  - a. Visual analogue scale (0-10) where 0=no pain, 10=worst imagineable pain every hour for the first 4 hours and then every 4 hours for the rest of the 24 postoperative hours. This will be done during rest and movement.
  - b. Total amount of IV morphine will be calculated at the end of the 24 postoperative hours.
  - c. Total amount of rescue analgesia will be calculated and first time of its need will be recorded.
2. Acute postoperative neuropathic pain will be detected 10 days after surgery by DN4 (Douleur Neuropathique 4) questionnaire (10 Questions with cut-off value 4/10).

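### Pain is the primary outcome, but no preoperative VAS, existing pain or regular analgesic use is listed as study data, so chance imbalance cannot be seen or adjusted for

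*Protocol*

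**What the plan says.** - **Primary outcome (Protocol, Aim of the Work):** "The primary outcome is the analgesic efficacy of the different local anaesthetic volumes of ESPB". The sample size paragraph under Patients sizes the trial on VAS: a difference of 2, SD 2.5, at least 15 per group, with 20 per group planned and 1:1:1 random allocation.
- **Eligibility (Protocol, Exclusion criteria):** of nine items, item 5, "Chronic opioid analgesic use", is the only one about earlier treatment for pain. Item 4, "Allergy or contraindication to any of the studied medications or anaesthetic agents", concerns tolerance of the study drugs. Item 2 removes patients with vertebral anomalies or earlier spinal surgery. No item names existing chest-wall, shoulder or arm pain, or regular non-opioid analgesics.
- **Preoperative visit (Protocol, Methods, Preoperative evaluation):** the day before surgery there is a general history and examination, and of the patients it says "they will be trained to use the visual analogue scale (VAS) which consists of 10 cm line". No score is asked for.
- **Baseline characteristics (Protocol, Measurements, item 1):** demographics "including age, sex and weight".
- **Pain data (Protocol, Measurements, item 4):** VAS at rest and on movement is taken "every hour for the first 4 hours and then every 4 hours for the rest of the 24 postoperative hours".
- **Baselines elsewhere:** vital signs are recorded before induction (item 2), and the cytotoxicity assay is done before the block (item 7).

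**The concern.** Existing pain and regular analgesic use may influence postoperative VAS, morphine use and the need for rescue. In a trial with 20 patients per arm such factors can fall unevenly by chance. Nothing among the eight groups of measurements would show whether they did, and no preoperative pain value is kept that could enter a model.

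Analysis detail may be left to a statistical analysis plan, but the choice of baseline data to collect has to be made before patients are enrolled. A later plan cannot recover a score that nobody wrote down. Two things are at stake: the ability to show that the arms were comparable on the factor closest to the primary outcome, and the precision gained by adjusting for it. The protocol already brings the patient and the VAS together on the day before surgery, so the information is lost for want of writing down two numbers.

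**Working it through.** **The plan's own figure.** The protocol gives 15 per group for a difference of 2, SD 2.5, F test, alpha 0.05, but states neither power nor the pattern of the three means. With 15 per group the F test has 58% power for means 0, 0, 2; 46% for 0, 1, 2; and 97% for 0, 2, 4. The 15 can therefore be neither confirmed nor refuted. The point here does not depend on it, because the working below uses the planned 20 per arm.

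**Inputs from the protocol.** n = 20 per arm, SD = 2.5, difference = 2, two-sided alpha 0.05.

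**Assumptions (not in the protocol).** Share of patients with existing pain or regular analgesic use p = 10-30%; such patients differ by 1-2 VAS points; correlation between preoperative and postoperative VAS r = 0.2-0.4.

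**Step 1: chance imbalance.** With X1 and X2 independent Binomial(20, p), the probability that two given arms differ by 4 or more such patients, and the probability that at least one of the three pairs of arms does:

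| p | Two given arms | Any pair of three |
|---|---|---|
| 10% | 6.3% | 14% |
| 20% | 16.4% | 34% |
| 30% | 22.6% | 45% |

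**Step 2: what such an imbalance does.** The shift in a contrast is 4/20 × (1 to 2 points) = 0.2 to 0.4 points. The standard error of a pairwise difference is sqrt(2 × 2.5² / 20) = 0.79. The shift is therefore 0.25 to 0.5 of one standard error, or 10-20% of the design difference of 2.

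**Step 3: precision gained by adjustment.** Residual variance is multiplied by 1 − r², so the residual SD is 2.5 × sqrt(1 − r²) and 20 per arm is worth 20/(1 − r²). Power is from the noncentral t distribution for two arms of 20, with 38 degrees of freedom unadjusted and 37 with the covariate.

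| r | 1 − r² | Residual SD | 20 per arm is worth | Pairwise power |
|---|---|---|---|---|
| unadjusted | 1 | 2.50 | 20 | 69% |
| 0.2 | 0.96 | 2.45 | 20.8 | 71% |
| 0.3 | 0.91 | 2.38 | 22.0 | 73% |
| 0.4 | 0.84 | 2.29 | 23.8 | 77% |

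A normal approximation gives about two points more throughout (72% unadjusted, 73% at r = 0.2, 76% at r = 0.3), so the gain is the same. If r is zero, the lost degree of freedom changes power only from 69.3% to 69.3% to one decimal.

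**The case against.** The strongest case against is that nothing here is wrong on its face. Excluding only chronic opioid users on pain grounds is a legitimate eligibility choice, allocation is random, and any chance imbalance is part of the sampling error that the significance level already allows for. The history taken the day before surgery may bring out pain and drug use, and item 5 can hardly be applied without asking about analgesics. Every driver of the size estimate is assumed.

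Most of this stands, and it limits the point in three ways.

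- A reader might infer that the comparison is **biased**. The documents do not support that: with 1:1:1 randomisation the unadjusted comparison is valid, and the illustrated shift is at most half of one standard error.
- A reader might infer that the **exclusions should be widened** to chronic regional pain and regular use of other analgesics. That is a trade-off between homogeneity and recruitment or generalisability, and the protocol does not get it wrong. Widening would also remove much of the variation in preoperative VAS that a covariate needs, so the gains in the working would not carry over.
- A reader might infer that prior pain and drugs will **go unrecorded altogether**. The text shows only that they are not listed as study measurements; the clinical history may contain them.

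What the objection does not remove is the missing data item. An unstructured clinical history is not a score in the study dataset, and the choice of baseline measurements is protocol content that an analysis plan cannot supply afterwards.

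**Conclusion.** The point holds as a low-cost improvement. Pain is the primary domain of this trial, yet it has no baseline among the listed measurements, while vital signs and cytotoxicity do. Balance on prior pain therefore cannot be shown, and adjustment for it is ruled out in advance.

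The size is modest: 20 per arm would be worth about 21 to 24, and pairwise power for a difference of 2 would rise from 69% to 71-77%. This rests on the protocol's SD of 2.5 and an assumed correlation of 0.2 to 0.4. The imbalance figures rest further on an assumed prevalence of 10-30% and an assumed effect of 1-2 points. Because pairwise power at 20 per arm is below 80% on the protocol's own difference and SD, a gain that needs no extra patients is worth taking. Leaving the protocol unchanged would not invalidate the result.

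**What to change.** 1. In the preoperative evaluation section, state that at the VAS training on the day before surgery a VAS at rest and a VAS on arm movement are recorded, together with any existing breast, chest-wall, shoulder or arm pain and any regular analgesic use, including gabapentinoids or antidepressants taken for pain.
2. Add these items to the Measurements section, and report them by arm with the other baseline characteristics.
3. State that postoperative VAS will be analysed with the matching preoperative VAS (rest for rest, movement for movement) as a covariate.
4. Leave the exclusion criteria unchanged.

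**Cost:** a few extra data items per patient at a visit already held, and one model degree of freedom per analysis. No patient is lost to eligibility. If most preoperative scores turn out near zero, the covariate will add little, but the record will still show whether the arms were comparable.

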### **Technique of ultrasound guided deep ESPB block:**

Ultrasound guided deep ESPB block will be performed in the block room at Medical Research Institute hospital. Patients will be placed in the prone position and a high-frequency linear probe (L 6-12MHz) of SonoSite, S nerve, 2 D machine, USA will be sterilized. After skin sterilization, the ultrasound probe will be placed 2.5–3 cm laterally to the spinous process in a parasagittal oblique plane, at the seventh cervical vertebra and moved caudally till T4.

After anatomical scanning and identification of the transverse process of T4 and the three muscles (Trapezius, Rhomboid major and Erector spinae), 2 ml of lidocaine 2% will be used to numb the skin then 18-gauge Tuohy needle will be advanced cranio-caudally towards the lateral border of transverse process of T4 using the in-plane technique.

The needle tip will be located in the fascial plane between the transverse process and erector spinae muscle. The correct needle position will be tested by injecting 2 ml of saline resulting in hydrodissection of the plane followed by the injection of:

- 20 ml bupivacaine 0.25% and 5 ml of radiocontrast dye (Omnipaque) in group 1.
- 40 ml bupivacaine 0.125% and 5 ml of radiocontrast dye (Omnipaque) in group 2.

Then, insertion of epidural catheter 2 to 3 cm over the tip of the Tuohy needle under real-time US guidance will be done.

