### **Postoperative analgesia:**

Bolus of bupivacaine, with the same volume and concentration assigned to each group, will be given in the epidural catheter at the end of surgery in groups I & II.

In the PACU, pain score (as with other measurements) will be assessed by a physician not involved in the study design.

Intravenous morphine patient controlled analgesia (PCA) will be prepared by 50 mg morphine +45 ml normal saline with a concentration of 1 mg morphine /1 ml.

1. Bolus dose of 0.05 mg/kg.
2. Lockout Interval: 10 minutes.
3. Four hourly limiting doses will be 10 mg.

If VAS still  $\geq 4$ , patients will be administered Ketorolac 30 mg IV as rescue analgesia.

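### Exclusion criterion 8 is worded as actual operating time over 90 minutes, which is known only after randomisation, so read literally it removes randomised patients on a post-randomisation event

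*Protocol*

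**What the plan says.** The protocol lists nine exclusion criteria. Item 8 is "Duration of surgery more than 90 minutes", and that is its full content.

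The other relevant statements are:

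- **Allocation (Patients section):** "Patients will be randomly allocated using a computer generated random table", in a 1:1:1 ratio. The moment of randomisation is not given.
- **Treatment (Patients section):** for group I, "20 patients will receive US-guided deep ESPB block before induction of general anaesthesia". Group II has the same timing, and group III has no block. The technique section adds: "Ultrasound guided deep ESPB block will be performed in the block room".
- **CT scan (Measurements, item 6):** done 15 minutes after the block, before induction and surgery.
- **Second bolus (Postoperative analgesia):** it "will be given in the epidural catheter at the end of surgery in groups I & II".
- **Sample size (Patients section):** "A minimal sample size of 15 in each group is required"; 20 per group are planned.
- **Screening (Preoperative evaluation):** "Evaluation of the patients will be carried out on the day before surgery". The section mentions no estimate of operating time.
- **Recorded data (Measurements):** there are eight headings. Demographics are described as "including age, sex and weight". Duration of surgery appears under none of the eight.

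**The concern.** An exclusion criterion should be decidable before a patient is randomised. Item 8, as worded, is not: it refers to how long the operation lasted. Anyone who applies it literally removes patients who have already been allocated and, in two of the three groups, already treated and scanned.

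Three things are at stake.

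1. **Comparability of the groups.** Randomisation protects the comparison only if the patients compared are those who were randomised. If overruns, or the decision to act on them, are related to the group, the remaining patients are no longer comparable. The protocol does not say who applies item 8, when, or whether that person knows the allocation. If it is applied some time after surgery, pain scores may already be known.
2. **The population.** The result would describe operations that turned out short, which cannot be identified in advance.
3. **Numbers.** If excluded patients are not replaced, and the protocol does not say, the exclusions use up the margin between 20 planned and 15 required per group.

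**Working it through.** **Step 1: order of events.** This follows from the protocol's own text.

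| Order | Event | Where stated |
|---|---|---|
| 1 | Evaluation on the day before surgery | Preoperative evaluation |
| 2 | Random allocation | Patients; time not given, but it must precede the allocated block |
| 3 | Block, groups I and II | Patients; block technique |
| 4 | CT, 15 minutes after the block | Measurements, item 6 |
| 5 | Induction and surgery | Anaesthesia |
| 6 | End of surgery: actual duration known; second bolus due in groups I and II | Postoperative analgesia |

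Item 8, read literally, can be decided only at row 6. The other eight exclusion criteria can all be judged by row 1 or 2.

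**Step 2: does another section supply the missing qualifier?** No. The Patients section describes patients as scheduled for mastectomy, but nothing attaches a scheduled or expected time to item 8. Nothing says what happens to a randomised patient whose operation passes 90 minutes.

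**Step 3: could the record show how the rule was applied?** Only roughly. Vital signs are taken before induction, every 15 minutes during surgery and on arrival in the PACU. Those times allow an approximate duration, but not a reliable one close to 90 minutes.

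**Step 4: size of the margin.** The plan's 15 per group cannot be reproduced definitively, because no power is stated. It is used here only as the plan's own threshold. The margin is 20 − 15 = 5 per group, or 5/20 = 25%.

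The protocol gives no overrun rate, so the rate *e* is an assumption and a range is shown. Further assumptions are the literal reading, no replacement, the same *e* in each group, and independence between patients and groups.

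- Expected loss over the trial: 60 × *e*.
- Chance that one group falls below 15: P = Pr(X ≤ 14), with X ~ Binomial(20, 1 − *e*).
- Chance that at least one of three groups does: 1 − (1 − P)³.

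| Assumed *e* | Expected loss of 60 | P, one group | At least one group below 15 |
|---|---|---|---|
| 5% | 3 | 0.0003 | 0.0010 |
| 10% | 6 | 0.0113 | 0.0334 |
| 15% | 9 | 0.0673 | 0.1886 |
| 20% | 12 | 0.1958 | 0.4799 |
| 25% | 15 | 0.3828 | 0.7649 |

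Worked line for 20%: 1 − (1 − 0.1958)³ = 1 − 0.8042³ = 1 − 0.5201 = 0.4799. The last column was computed from unrounded P.

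The chance that at least one group falls short reaches 5% at an overrun rate of 10.9%, and 50% at 20.3%.

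**Step 5: bias.** No size can be given. The protocol has no information on how operating time, or the use of item 8, might differ between groups.

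**The case against.** The strongest reply is that item 8 sits in a list of baseline criteria, for patients already scheduled for surgery, and so most naturally describes which operations are eligible. The protocol nowhere says that a randomised patient will be withdrawn, dropped from the analysis or replaced. On that view, one word is missing and the rest is conjecture about conduct. This stands in part: planned duration may well have been meant. But the text does not say so, and it permits the harmful reading as readily as the harmless one.

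Second, no mechanism is shown by which operating time would differ by group, and the protocol states that research personnel are blinded throughout. If overruns are unrelated to allocation and the rule is applied mechanically, the loss costs patients without biasing the comparison. That is correct, and so only potential bias is claimed. Blinding reduces the risk of selective use but does not settle it, because the protocol does not say who applies item 8, and groups I and II have a catheter that group III lacks.

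Third, every overrun rate is assumed, and 15 is not a validated failure point. With SD 2.5 and alpha 0.05, 15 per group gives an F-test power of 0.46 for means 0/1/2, 0.58 for 0/0/2 and 0.97 for 0/2/4. This also stands. The probabilities illustrate the margin; the point does not rest on them.

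Fourth, analysis sets and sensitivity analyses may be left to an SAP that is not shown. That is fair in general. But when eligibility is judged belongs in the protocol, and keeping patients whose surgery overruns follows directly from making item 8 a pre-randomisation criterion.

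**Conclusion.** The concern holds. As written, item 8 excludes randomised patients on an event known only after randomisation, and nothing in the protocol turns it into a preoperative judgement. That conclusion rests on the wording and on the order of events, with one inference: allocation precedes surgery because the allocated block is given before induction.

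The size of any bias cannot be derived. The effect on numbers is negligible if overruns are rare, staying under a 5% chance of any group dropping below 15 until about 11% of operations overrun. It becomes substantial at 20% or more, under the assumptions of no replacement and equal, independent rates. If planned duration was intended, what remains is an ambiguity that still lets the rule be applied after treatment. The point should be fixed: its effect is uncertain, but the wording is wrong for its purpose and the cure is nearly free.

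**What to change.** - Reword item 8 so that it refers to surgery scheduled or expected to last more than 90 minutes, judged before randomisation, for example at the evaluation on the day before surgery. The 90-minute limit stays as it is.
- Add a sentence that a randomised patient whose operation runs longer is not excluded, and stays in the primary analysis in the allocated group.
- Add actual duration of surgery to the listed measurements. If an analysis restricted to operations of up to 90 minutes is wanted, use it only as a sensitivity analysis.

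The cost is one line of eligibility wording, one sentence and one recorded item. The small downside is that a few long operations stay in and may add some variance.
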